12.8. INTERIM ANALYSIS

This is an initial exploratory study of TP-03 for this indication. If needed for business or project planning purposes including the design of any future studies, Tarsus may perform an interim analysis once 20 or more participants have been enrolled in the study.

12.9. FINAL REPORT

Once all participants have completed the Day 85 assessment or have been exited from the study and all corresponding data has been received and corrected, the study database for visits through Day 85 will be locked. Once the data has been locked, the treatment assignments will be unmasked and a complete analysis of the results will be performed and a final report will be prepared. Once all participants have been exited from the study and all additional data has been received and corrected, the complete database including the additional data collected through Day 115 will be locked. An addendum to the final report will be prepared to include the additional follow-up results through the Day 115 assessment.

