8.5. DAY 115 (+60 DAYS)

Participants who were exited from the study after completing dosing of study drug through Day 85 and participants who have not exited the study will be invited for an additional post-treatment follow-up visit on Day 115.

Procedures to be performed include:

- Reconsent the participants who were exited per protocol version 3.0 and participants who have not exited the study
- Concomitant medications review
- CDVA
- Slit lamp biomicroscopy including assessment of lid margin erythema
- Meibomian gland secretion assessment of lower lids
- Assessment of adverse events
- Study exit

At this visit, participants will be exited from the study provided they do not have any ongoing adverse events.

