11. EARLY TERMINATION AND PARTICIPANT DISCONTINUATION

For each participant, the study will be considered completed when the Day 115 assessment has been performed in accordance with the study protocol.

Any participant may voluntarily discontinue the study at any time without prejudice. The investigator may elect to discontinue a participant for reasons unrelated to the study drug (e.g., failure to comply with the study protocol, missed visits, etc.) or for reasons related to the study drug (e.g., AE, unsatisfactory therapeutic response, etc.). Reason(s) for discontinuation should be recorded on the CRF.

Clinical Research Protocol

Protocol TRS-008

01-Feb-2023

Possible reasons for study discontinuation include the following:

- Lack of efficacy: the participant does not feel that the study drug has adequately relieved his/her symptoms
- AEs necessitating discontinuation from the study
- The participant is lost to follow-up
- Participant decision unrelated to lack of efficacy or AEs
- Reasons relating to COVID-19
- Investigator decision (specify)
- Other reason (specify)

If a participant chooses to discontinue his/her participation or is discontinued, the Exit Form will be completed regardless of other information available. Should a participant experience any difficulties requiring review between planned visits, or in case of early exit between planned visits, the Unscheduled Visit Form will be completed. Reason(s) for such a visit will be recorded on the CRF. Discontinued participants will not be replaced. Participants to be discontinued for AE(s) will be followed until the event is resolved, if possible, or considered medically stable by the investigator.

The data to be collected at the time of study treatment discontinuation may include the following:

- An AE assessment and performance of safety assessments including visual acuity and slit lamp biomicroscopy
- Any follow-up evaluations required per investigator determination

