12.2. RANDOMIZATION

This is a randomized, double-masked study. A blocked randomization schedule will be prepared and used to package the afternoon dose of the drug (all participants receive TP-03 for the morning and evening doses). The drug will be dispensed at the site sequentially from the available inventory. The bottle number dispensed will be recorded.

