12.5 STUDY OUTCOMES

Efficacy outcomes for this study will include:

- Total meibomian gland secretion score (MGSS) computed as the sum of the grades for all 15 glands evaluated on the lower eyelid with a range from 0 to 45.

- Lid margin erythema

The primary safety endpoint of this study is incidence of treatment-related adverse events (AE). Descriptive statistics of adverse events will be provided, as will narratives of any serious, unexpected, drug-related AEs. Any clinically meaningful changes in visual acuity or slit lamp biomicroscopy findings will be tabulated.

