13. ETHICAL AND REGULATORY CONSIDERATIONS

Investigator Responsibilities/Performance (Code of Conduct): The investigator will ensure that the clinical study is conducted in accordance with the ethical principles that have their origin in the Declaration of Helsinki, GCP, ICH guidelines and any regional or national regulations as appropriate. The investigator will also ensure that participants undergo no investigational procedures other than those described in this protocol and approved by the IRB, except those procedures deemed necessary to protect the health and well-being of the participant. Any such procedures will be documented in the participant's records and reported to the IRB as required. If any additional requirements are imposed by the IRB or regulatory authority, these requirements shall be followed.

Informed Consent Process and IRB:

The site will submit the proposed informed consent to the IRB for review and approval. Copies of the informed consent form used in the study should contain the IRB-approved stamp (if applicable) and version date. The following information should be provided in the informed consent:

- The study is research and the purpose of the research

- Purpose of the study including the potential duration of participation by the participant and a description of the procedures
- Possible side effects, risks or discomforts of the investigational drug
- Reasonably expected benefits
- The existence of alternative therapy options and/or alternatives to participating in the study
- Confidentiality of records and possible inspection of records
- Costs, compensation and treatment for injury
- Person to contact regarding participant's rights
- Person to contact for questions on research or research-associated injury
- Participation is voluntary
- The right to discontinue participation in the study at any time without disadvantage to the participant
- Participant will be informed of new information learned during the study, which may affect the participant's decision to continue participation in the study

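### Does unmasking after the Day 85 lock, with no roles named, compromise the Day 115 follow-up?

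*Protocol*

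**What the plan says.** Protocol section 12.9 sets the order of events. When every participant has completed Day 85 or left the study, and those data are in and corrected, the database through Day 85 is locked. Then: "Once the data has been locked, the treatment assignments will be unmasked and a complete analysis of the results will be performed". A final report follows. Later, when everyone has exited and the remaining data are in and corrected, "the complete database including the additional data collected through Day 115 will be locked", and an addendum reports the extra follow-up.

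Section 8.5 describes the late visit. Participants "will be invited for an additional post-treatment follow-up visit on Day 115", including those who had already exited under protocol version 3.0. The visit repeats the secretion grading, the adverse event assessment and "Slit lamp biomicroscopy including assessment of lid margin erythema". Under section 11, for each participant "the study will be considered completed when the Day 115 assessment has been performed".

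Section 12.2 calls the study double-masked. It explains that the randomization governs only the afternoon bottle, since "all participants receive TP-03 for the morning and evening doses". It does not list who is masked or until when. The SAP contents page lists a section 2.2.3 on randomization and masking, but its text was not available for this review. The visit list in the SAP's protocol summary stops at Day 85.

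**The concern.** The unmasking sentence is passive and names no one. Read literally, codes could become generally known at the Day 85 lock while examiners are still grading at Day 115 and data staff are still correcting those records.

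The outcomes involved depend on judgement. Gland secretion and lid margin erythema are examiner grades. Relatedness of an adverse event is decided by the examining clinician (section 16.3.2), and treatment-related events form the primary safety endpoint (section 12.5). The stated clinical hypothesis expects TID to improve more than BID without a significant increase in irritation, so an unmasked examiner would hold a directional expectation. Bottle numbers are recorded at dispensing, so a schedule that reached a site could be matched to individuals. Section 16.7 also makes the principal investigator responsible for telling participants study-related results, which gives a Day 85 report a written route to sites and participants.

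If codes did reach examiners or participants before Day 115, a BID-TID comparison in the addendum could be biased.

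**Working it through.** **Inputs.** Day 85 window −13/+7 days (Protocol 8.4). Day 115 window +60 days (8.5). Maximum time in study 175 days (10.4). Adverse event recording to 7 days (non-serious) or 30 days (serious) after the last day of participation (16.4). The time from the last Day 85 visit to the first lock is not stated.

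**The plan's own figure.** 115 + 60 = 175, which agrees with section 10.4.

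**Gap between the two visits.**
- Day 85 visit: 85 − 13 = Day 72 to 85 + 7 = Day 92.
- Day 115 visit: Day 115 to Day 175.
- Shortest gap: 115 − 92 = 23 days. Longest gap: 175 − 72 = 103 days.

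**When unmasking could precede a Day 115 visit.** Let L be the days from the calendar date of the last Day 85 visit to unmasking. Suppose that last visit falls on the participant's study day d, with d between 72 and 92. The participant's Day 115 window opens 115 − d days later (23 to 43) and closes 175 − d days later (83 to 103).
- L below 23: this participant's Day 115 visit, if attended, comes after unmasking.
- L above 103: no in-window Day 115 visit does, because every other Day 85 visit was on or before that date. Correction of Day 115 records could still be open.
- L from 23 to 103: it depends on the actual dates.

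Below 23 days, overlap is certain only for the participant seen last, and only if that person returns. Participants who finished Day 85 earlier, including those who had exited under version 3.0, may have attended Day 115 before the lock.

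**Adverse event tail.** If participation ends by Day 175, non-serious events are recorded to 175 + 7 = Day 182, which is up to 182 − 72 = 110 days after the Day 85 visit. Serious events are recorded to 175 + 30 = Day 205, up to 205 − 72 = 133 days after it. These are not strict limits, because section 8.5 makes exit conditional on there being no ongoing adverse events. They also say nothing about the grades.

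**What must happen for harm.** All of the following are needed:
1. The first lock falls before some Day 115 assessments. The windows permit this; the documents do not show it.
2. Codes reach an examiner, a participant or someone correcting data. No readable text provides for this.
3. That knowledge alters a grade, a report or a relatedness rating.
4. The addendum compares the regimens on those data. Section 12.7 names no visit, and section 12.9 says only that the follow-up results will be included.

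**Reading the sections together.** Section 12.9 sits within the statistical chapter and ties unmasking to an analysis and a report. Section 12.2 sets no time limit on masking, and section 11 ends a participant's study at Day 115. Together these imply that examiners and participants stay masked through Day 115 unless something lifts it, and nothing readable does.

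**The case for a change.** The strongest case for a change is that the remedy is cheap. One or two sentences in section 12.9 could limit participant-level codes to the analysis team until the second lock, without altering a visit, a number or the Day 85 timeline. The results are meant to inform later studies (section 12.1), so a Day 115 comparison should be interpretable. The SAP's definition of a treatment-emergent event gives no end date, so events arising after the first lock can still count. And since the SAP's visit list ends at Day 85, any restriction in SAP 2.2.3 might not reach Day 115.

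All of this stands as a reason why such a sentence would do no harm. It does not show a defect. The silence at issue cannot be established while SAP 2.2.3 is unread, and unavailable text cannot be counted as absent from the plan. Section 16.7 concerns results rather than individual codes. Changes to grades already recorded are limited by source verification and data clarification requests (section 19). Any restriction would also need to leave room for aggregate Day 85 results, for safety information, for results under section 16.7, and for the section 13 commitment: "Participant will be informed of new information learned during the study".

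**Conclusion.** No change to the plan is needed. Leaving the unmasked roles out of section 12.9 is a missing detail that a trial team fills sensibly: the code is opened for those doing the Day 85 analysis, and sites and participants stay masked to the end of follow-up. SAP 2.2.3 may already say so.

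The effect on the Day 85 analysis is nil, because those data are locked before unmasking. The remaining exposure is the Day 115 grades, adverse events recorded after the first lock, and the addendum. These concern off-treatment follow-up by invitation in a pilot of up to 40 participants, with safety summarized descriptively and without inferential testing (SAP 2.2.9). The code itself reveals only whether the afternoon bottle was active.

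Overlap is certain for the last-seen participant, if that person returns, when unmasking comes fewer than 23 days after the last Day 85 visit. It is ruled out for Day 115 visits beyond 103 days. Both figures assume visits within their windows. The actual interval is not stated, and the documents give no basis for a bias size. The conclusion would be different if codes were in fact released to sites or participants before their Day 115 visits, but nothing readable provides for that.

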13. ETHICAL AND REGULATORY CONSIDERATIONS

Investigator Responsibilities/Performance (Code of Conduct): The investigator will ensure that the clinical study is conducted in accordance with the ethical principles that have their origin in the Declaration of Helsinki, GCP, ICH guidelines and any regional or national regulations as appropriate. The investigator will also ensure that participants undergo no investigational procedures other than those described in this protocol and approved by the IRB, except those procedures deemed necessary to protect the health and well-being of the participant. Any such procedures will be documented in the participant's records and reported to the IRB as required. If any additional requirements are imposed by the IRB or regulatory authority, these requirements shall be followed.

Informed Consent Process and IRB:

The site will submit the proposed informed consent to the IRB for review and approval. Copies of the informed consent form used in the study should contain the IRB-approved stamp (if applicable) and version date. The following information should be provided in the informed consent:

- The study is research and the purpose of the research

- Purpose of the study including the potential duration of participation by the participant and a description of the procedures
- Possible side effects, risks or discomforts of the investigational drug
- Reasonably expected benefits
- The existence of alternative therapy options and/or alternatives to participating in the study
- Confidentiality of records and possible inspection of records
- Costs, compensation and treatment for injury
- Person to contact regarding participant's rights
- Person to contact for questions on research or research-associated injury
- Participation is voluntary
- The right to discontinue participation in the study at any time without disadvantage to the participant
- Participant will be informed of new information learned during the study, which may affect the participant's decision to continue participation in the study

The investigator or qualified/delegated staff will obtain written informed consent from each participant prior to the initiation of any study-related activities. The potential study participant or the participant's legally authorized representative will be allowed sufficient time to thoroughly read (or have read and explained to them) the informed consent form. The investigator or qualified/delegated staff will answer any questions that the potential study participant or their representative might have. If the potential study participant agrees to participate in the study, all required parties should sign and date the informed consent form. The original signed informed consent form will be retained by the site and a copy will be given to the potential study participant for their records. The obtaining of informed consent and the date of that informed consent should be noted in the participant's medical notes. It should also be noted that informed consent was obtained prior to any study-related activities being conducted.

14. INVESTIGATOR RESPONSIBILITIES

The investigator will ensure that the clinical study is conducted in accordance with Good Clinical Practice (GCP), International Conference on Harmonisation (ICH) and all regulatory and institutional requirements, including those for participant privacy, informed consent, Institutional Review Board approval and record retention.

The investigator is responsible for any expedited reports of SAEs or SUSARs to the regulatory authorities and IRB.

15. CONCOMITANT MEDICATIONS AND THERAPIES

All concomitant medications including over-the-counter medications and nutritional supplements used within 3 months prior to the first visit will be documented. Any changes to concomitant medication use or the initiation of new medications will be reported throughout the study. For the duration of the study, any therapy considered necessary for the maintenance of participant welfare may be given to the participant at the discretion of the investigator. Initiation of new medications, changes to concomitant medications, or new therapies administered to the participant should be recorded on the appropriate case report form. In the event prohibited medications / procedures are indicated for care as a medical necessity, participants will not be discontinued.

If participants experience significant symptoms of dry eye during the study, participants will be allowed to use a sterile saline solution as necessary provided by the investigator, but participants will be instructed not to use the drop for at least one hour before and one hour after administration of the study drug. On the day of in-office study visits, participants should be advised not to use the sterile saline solution prior to the visit; the saline solution can be used after the visit has been completed. The use of nutritional supplements is not restricted.

15.1. PROHIBITED CONCOMITANT MEDICATIONS/PROCEDURES

No other experimental drug or device should be used within three months of the Day 1 visit or during the course of the clinical trial.

Study participants will be asked not to use any topical ophthalmic medications one hour before and one hour after administration of the study drug. In addition, participants should refrain from using any cosmetics (e.g., eyeliner, mascara, foundation or eyeshadow) in the vicinity of the eyelid margin on the day of their visit prior to completion of the visit.

Contact lenses should not be worn for the duration of the study.

- Artificial eyelashes, eyelash extensions or other cosmetic eyelash or eyelid procedures

16. ADVERSE EVENTS AND SERIOUS ADVERSE EVENTS

16.1. DEFINITION OF ADVERSE EVENTS (AE)

Adverse event is defined as any untoward medical occurrence associated with the use of a drug in humans, whether or not considered drug-related (21 CFR 312.32 (a)).

16.2. DEFINITION OF SERIOUS ADVERSE EVENTS (SAE)

An AE or suspected adverse reaction is considered “serious” if, in the view of either the investigator or sponsor, it results in any of the following outcomes: death, a life-threatening AE, inpatient hospitalization or prolongation of existing hospitalization, a persistent or significant incapacity or substantial disruption of the ability to conduct normal life functions, or a congenital anomaly/birth defect. Important medical events that may not result in death, be life-threatening, or require hospitalization may be considered serious when, based upon appropriate medical judgment, they may jeopardize the participant and may require medical or surgical intervention to prevent one of the outcomes listed in this definition. Examples of such medical events include allergic bronchospasm requiring intensive treatment in an emergency room or at home, blood dyscrasias or convulsions that do not result in inpatient hospitalization, or the development of drug dependency or drug abuse. Serious adverse events include drug deficiencies that might have led to an SAE if a) suitable action had not been taken or b) intervention had not been made or c) if circumstances had been less fortunate.

Events that are considered sight-threatening in the opinion of the investigator will be considered SAEs.

A planned hospitalization for a pre-existing condition without a serious deterioration in health is not considered to be an SAE. Hospitalization for less than 24 hours is not considered an SAE unless the precipitating event was unanticipated and also related to the investigational drug.

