16.6. SERIOUS ADVERSE EVENT REPORTING

The study clinician will immediately report to the sponsor and Medical Monitor any SAE, whether or not considered study treatment-related, including those listed in the protocol or Investigator’s Brochure and must include an assessment of whether there is a reasonable possibility that the study treatment caused the event [21 CFR 312.64(b)]. Serious adverse events must be reported immediately to the below-listed individuals using the Serious Adverse Event Report (SAER) form. Sites will also be instructed to document the event in the Serious Adverse Event eCRF.

All SAEs will be followed until satisfactory resolution or until the site investigator deems the event to be chronic or the participant is stable. Other supporting documentation of the event may be requested by the study sponsor and should be provided as soon as possible.

The study sponsor or designee will be responsible for notifying the Food and Drug Administration (FDA) of any unexpected fatal or life-threatening suspected adverse reaction as soon as possible, but in no case later than 7 calendar days after the sponsor's initial receipt of the information [21 CFR 312.32I(2)]. In addition, the sponsor must notify the FDA and all participating investigators in an Investigational New Drug (IND) safety report of potentially serious risks from clinical trials or any other source as soon as possible, but in no case later than 15 calendar days after the sponsor determines that the information qualifies for reporting [21 CFR 312.32I(1)]. In each IND safety report, the sponsor must identify all IND safety reports previously submitted to the FDA concerning a similar suspected adverse reaction and must analyze the significance of the suspected adverse reaction in light of previous, similar reports or any other relevant information. The sponsor must report any suspected adverse reaction that is both serious and unexpected. The sponsor must report an AE as a suspected adverse reaction only if there is evidence to suggest a causal relationship between the drug and the AE.

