2.2.9.1.1 Serious Adverse Events

The number and percentage of subjects experiencing a Serious Adverse Event (SAE) will be tabulated by SOC and PT by dosing regimen and overall. SAEs will be counted only once for a subject within each PT and SOC.

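### Protocol 16.2 makes the seriousness of a hospital stay under 24 hours depend on relatedness and anticipation, so SAE reporting and counts can miss short admissions; its drug-deficiency clause can inflate the counts.

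*Protocol*

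**What the plan says.** Protocol 16.2 lists the outcomes that make an event serious. One is "inpatient hospitalization or prolongation of existing hospitalization", with no minimum length of stay and no causality condition. Other routes are death, a life-threatening event, an important medical event in medical judgment, and a sight-threatening event. One example of an important medical event is "allergic bronchospasm requiring intensive treatment in an emergency room or at home", which needs no admission.

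The section closes with an exclusion: "Hospitalization for less than 24 hours is not considered an SAE unless the precipitating event was unanticipated and also related to the investigational drug". It also contains an extension: "Serious adverse events include drug deficiencies that might have led to an SAE if a) suitable action had not been taken", followed by two further hypothetical conditions.

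Four other places bear on this:

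- Protocol 16.1 defines an adverse event as "any untoward medical occurrence associated with the use of a drug in humans, whether or not considered drug-related".
- Protocol 16.3.3 has expectedness determined for events already characterized as related and serious.
- Protocol 16.4 sets the recording period after the last day of participation at 7 days for non-serious events and 30 days for SAEs.
- Protocol 16.6 requires immediate reporting of "any SAE, whether or not considered study treatment-related".

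SAP 2.2.9.1 gives subject counts and percentages for SAEs and for drug-related SAEs, by regimen and overall. SAP 2.2.9.1.1 adds: "The number and percentage of subjects experiencing a Serious Adverse Event (SAE) will be tabulated by SOC and PT". The readable SAP text has no SAE definition of its own, so the tables inherit the protocol's.

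**The concern.** Seriousness, causality and expectedness are normally three separate judgments, and 16.3 and 16.6 otherwise treat them that way. The 24-hour sentence merges them. Whether a short admission is serious turns on the site's view of relatedness and anticipation, and events that fail either test never reach the SAE reporting route. The sponsor would then not receive the prompt report that would let it question the site's causality call.

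Three things depend on SAE status: immediate reporting (16.6), the length of the collection period (16.4), and the SAP's SAE and drug-related SAE tables. The deficiency clause works the other way. It can put into those tables an occurrence in which no SAE, and possibly no adverse event, took place.

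**Working it through.** There is no planned figure to reproduce. The documents state no expected SAE rate, and safety is summarized without testing. The check is therefore a comparison of the texts, followed by a note on scale.

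**Step 1. Apply the 24-hour sentence to every kind of short inpatient stay.** The two conditions are joined, so both must hold for the stay to count. The table takes stays that meet no other seriousness criterion.

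| Short stay | Serious under the hospitalization criterion? | SAE after the 24-hour sentence? | Lost from SAE count? | Lost from drug-related SAE count? |
|---|---|---|---|---|
| Related, unanticipated | Yes | Yes | No | No |
| Related, anticipated | Yes | No | Yes | Yes |
| Unrelated, unanticipated | Yes | No | Yes | No (never in it) |
| Unrelated, anticipated | Yes | No | Yes | No (never in it) |

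Three of the four kinds lose SAE status. Only one of them would have been in the drug-related SAE count, because SAP 2.2.9.1 confines that count to events rated definitely or potentially related.

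**Step 2. Check the order of judgments.** Section 16.3.3 assesses expectedness once an event is known to be related and serious. For a short stay, 16.2 needs a view on anticipation before seriousness can be settled. Moreover, 16.3.3 explains what unexpected means, while the term used in 16.2, unanticipated, has no definition in the readable text. A site cannot apply the two sections in the order written.

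**Step 3. Check precedence.** The 24-hour sentence does not say whether it qualifies only the hospitalization criterion or overrides the life-threatening, important-medical-event and sight-threatening routes. Under the first reading, a 20-hour admission for a severe allergic reaction could still be serious by another route. Under the second it is excluded if anticipated, although 16.2's own example treats comparable care in an emergency room or at home as serious.

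**Step 4. Follow the recording window.** A short stay classed as non-serious falls under the 7-day limit in 16.4 instead of the 30-day limit. If it starts on days 8 to 30 after the last day of participation, it need not be recorded. Later reclassification cannot recover an event that was never collected. A short stay within the 7-day limit is still captured as an adverse event.

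**Step 5. Check the deficiency clause.** Section 16.2 begins from an adverse event or suspected adverse reaction, and 16.1 requires a medical occurrence. A deficiency with no such occurrence does not meet 16.1, yet 16.2 calls it an SAE. The readable SAP has no rule that sets such cases apart.

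**Step 6. Scale.** Inputs: up to 40 participants (protocol section 5) allocated 1:1 (protocol summary), so about 20 per arm at full enrolment.

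- One participant in an arm: 1/20 = 5 percentage points.
- One participant overall: 1/40 = 2.5 percentage points.

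The chance of at least one misclassified participant among 40 is 1 − (1 − p)^40, where p is the per-participant rate. The documents give no value of p, so these are assumptions shown as a range:

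| Assumed p | Chance of at least one in 40 |
|---|---|
| 0.5% | 18% |
| 1% | 33% |
| 2% | 55% |
| 5% | 87% |

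**The case against.** The strongest defence is that the 24-hour sentence, like the neighbouring one on planned hospitalization, merely qualifies the hospitalization criterion. On that reading all other routes to seriousness stay open, and 16.2 lets either the investigator or the sponsor judge an event serious. This is a fair reading, and it would rescue some short stays. The text does not state it, however, and even on that reading unrelated and related-but-anticipated stays that meet no other criterion are still excluded.

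Second, 16.6 governs what happens after classification and does not define seriousness. That is correct. A reader might infer a flat contradiction between 16.2 and 16.6, but the conflict is one of purpose: a relatedness test has been placed upstream of a rule meant to ignore relatedness. The direct textual conflict is within 16.2, between the hospitalization criterion and the 24-hour sentence.

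Third, the SAP builds one SAE table from adverse events that the investigator judged serious, so a deficiency without an adverse event might never enter it. That is possible, and the clause errs towards over-reporting. It is the smaller of the two problems. A reader might also infer that these deficiencies harmed nobody or could not be coded. Section 16.2 implies only that no SAE resulted, so lesser harm is possible, and nothing in the documents addresses how they would be coded.

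Fourth, the 5-point figure is true of any single event in an arm of 20. It shows scale and is not evidence that misclassification will occur.

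**Conclusion.** The inconsistency is real and rests on readable text. SAE counts **can** be too low because of the short-stay rule and too high because of the deficiency clause. The drug-related SAE count can lose only related-but-anticipated short stays, and can gain a deficiency only if it is rated definitely or potentially related. The most lasting consequence is the possible non-recording of short admissions that start 8 to 30 days after participation ends.

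A reader might infer that the counts **are** wrong in both directions. The documents do not support that: an affected event must first occur among at most 40 participants, no rate is given, and some short stays may qualify by another route. Nor do they support the inference that unrelated short stays distort the drug-related SAE count.

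The primary safety endpoint (protocol 12.5) is the incidence of treatment-related adverse events and does not use seriousness. Safety is descriptive only (SAP 2.2.9), so no error rate or power is affected. The size, 5 points per arm of 20 or 2.5 points in 40 for each misclassified participant, assumes full enrolment, equal arms and all participants in the denominator.

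**What to change.** 1. In protocol 16.2, delete or rewrite the whole 24-hour sentence so that seriousness does not depend on relatedness or expectedness, and reconcile it with the hospitalization criterion and with 16.3.3 and 16.6. Removing only the *unless* clause would be worse than the present text: it would leave an unconditional exclusion of all stays under 24 hours and lose the related, unanticipated ones as well.
2. If any short-stay exclusion is kept, state that it qualifies only the hospitalization criterion and does not apply when another seriousness criterion is met.
3. Keep reporting drug deficiencies without an adverse event to the sponsor, but list them separately from the SAE tables in SAP 2.2.9.1 and 2.2.9.1.1, and align 16.2 with 16.1 accordingly.

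The cost is a wording amendment, a notice to sites and one line in the SAP. The downside is that a few more short admissions will be reported as SAEs.
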